7.5.2.3 Interruption or Discontinuation of Infusion

If a subject experiences a clinically significant Grade 3 or 4 AE considered by the Investigator to

be related to the study drug or due to infusion procedure, the infusion will be stopped. Infusion

may be restarted at the Investigator's discretion if the AE responds to medical management;

otherwise, the infusion should be discontinued permanently.

Should an interruption of the infusion be due to observed mass effect / increased intracranial

pressure (ICP), treatment with mannitol is suggested (see Table 3) with infusion resuming after

recovery (if possible), such that it can be completed within the maximum infusion duration window

of approximately 48 hours.

Treatment may be discontinued at the discretion of the Investigator. In the unlikely event that all

catheters are placed erroneously (not in line with placement guidelines in section 6.3) or cannot

be used (e.g. catheters do not function/convect), the procedure will be halted and no infusion

given to the subject.

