- j Baseline conditions/symptoms will be collected from Screening until Day 0 before subject is anesthetized for catheter placement surgery; any baseline condition or symptom noted prior to catheter placement will be recorded in the Medical History

k

- I see Study Pharmacy Manual for infusate preparation and dispensing instructions
- m Following completion of infusion (only after the end of infusion MRI and at any time prior to subject's discharge from the hospital), the catheters can be removed and the incisions closed in accordance with institutional practice. Removal of catheters must be performed by a delegated neurosurgeon.
- n All concomitant medications will be collected on the Electronic Data capture (EDC) system from the date of informed consent through 30-day safety period. Thereafter, concomitant medications associated with treatment-related SAEs and detailed anti-tumor therapy will be collected. Corticosteroid use will be collected until Day 360 or early withdrawal.
- All AEs will be collected from catheter placement through the end of study visit and all AEs and SAEs will be followed until resolution, stabilization, data cut-off, or death
- Subjects who complete the Day 360 assessment without disease progression or discontinue early without disease progression will continue to be followed for disease status until progression. After progression (documented on study or during post-study follow-up), subjects will continue to be followed for survival, post-study treatment(s) for GB and imaging for GB, where possible, until death (or termination of data collection by the Sponsor or withdrawal of consent by the subject).
- q Physical exam and KPS assessments will be performed after completion of infusion when the subject is ambulatory prior to hospital discharge
- Vital signs monitoring (without weight parameter) will be performed according to institutional best practice throughout entire surgical workflow for catheter placement and CED infusion; study specific vital signs check points during the surgical workflow are prior to initiation of anesthesia, following placement of all catheters but prior to patient being loaded into MRI machine for the real-time infusion monitoring segment and approximately 1 hour post initiation of infusion; NOTE: Site will record any abnormal vitals observed at any time during surgical vital signs monitoring as unscheduled findings.

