- Collection of blood sample for PK analysis (baseline)

Concomitant medications and treatments will be recorded from 14 days before infusion (Day 0) until the Day 360 (or early termination) visit, and AEs will be recorded from the time of signing the informed consent document until the Day 360 (or early termination) visit.

In addition, a serum pregnancy test must be performed within 14 days before infusion (Day 0) for all female subjects of childbearing potential.

While the above assessments are being carried out, screening MRI will be subject to review by CED experts pertaining to evaluation of suitability of tumor for convection. The screening MRI will also be sent to an independent central assessment of objective radiologic tumor characteristics.

Subjects will be approved for enrollment by the Medical Monitor following comprehensive review all screening results.

Following approval of subject for enrollment, Investigator/site will be notified and preliminary pretreatment catheter trajectory planning using CT scan and screening MRI (registered with iPlan® Flow Infusion planning software) can ensue (see Section 6.3 for catheter placement guidelines).

NOTE: use of iPlan® Flow software is required for catheter trajectory planning.

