8.2 Evaluation of Safety

Each subject receiving MDNA55 via CED will be evaluable for safety. Safety parameters include all laboratory tests and hematological abnormalities, physical findings, ECG, imaging parameters and AEs.

Each subject will be assessed periodically for the development of any toxicity as outlined in Section 7.5.

Definitions and reporting procedures for AEs provided in this protocol comply with current ICH E6 and other applicable international and local regulatory requirements. The Medical Monitor will promptly review all information relevant to the safety of MDNA55. The Investigator will carefully monitor each subject throughout the study for AEs and all AEs will be followed until adequately resolved. CTCAE 4.0 will be used to determine severity of AEs and SAEs.

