9.2.2.1 Intent to Treat (ITT)

An ITT population will comprise all subjects who receive any amount of study drug will be used for the primary efficacy analyses, other purely survival-based endpoints and all safety analyses.

A modified ITT population for secondary imaging-based analyses, including PFS, (mITT, see below) will comprise all subjects who receive any amount of study drug and have adequate imaging or clinical data for the ORR analysis. NOTE: Patients who expire or progress clinically prior to the first MRI examination will not be evaluable for any of the response assessments.

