9.2.2.4 Safety Population

The Safety population will comprise all patients treated on study. Safety analyses will be presented on this population.

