5. STUDY POPULATIONS

5.1 Intent to Treat Population (ITT)/Safety

An ITT population will comprise all subjects who sign the ICF and who receive any amount of study drug.

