6.2 Handling of Missing or Incomplete Date

To handle missing or partial AE and concomitant medication dates, the following rules will be applied.

For partial start dates:

- 1. If the month is unknown, then:
 - a) If the year matches the year of the dose date, then impute the month and day of the dose date.
 - b) Otherwise, assign "January."
- 2. If the day is unknown, then:
 - a) If the month and year match the month and year of the first dose date, then impute the day of the dose date.
 - b) Otherwise, assign "01."

For partial end dates:

- 1. If the month is unknown, then assign "December."
- 2. If the day is unknown, then assign the last day of the month.

After implementing the rules above, to determine whether AEs (or medications) with missing start or stop dates are pretreatment or on/after treatment, the following strategy will be used:

- 1. If the start date and stop date are both missing, then the most conservative approach is taken and the AE (or medication) is treatment emergent (or concomitant medication).
- 2. If the start date is missing but the stop date is not missing and is on or after the day of catheter placement, then the most conservative approach is taken and the AE (or medication) is treatment emergent (or concomitant medication).
- 3. If the start date is missing but the stop date is not missing and is before catheter placement and after the date of signed informed consent, then the medication is before treatment (or prior medication). Note: this is not applicable to AEs as all AE collection start from date/time of catheter placement.
- 4. If the start date is not missing but the stop date is missing, then the most conservative approach is taken, and medication concomitant while the AE is defined by start date.

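### Procedural adverse events in subjects who have catheters placed but receive no infusion would be recorded, yet left out of the planned safety summaries

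*Protocol*

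**What the plan says.** **When event collection starts.** Note o to Protocol Table 7 says "All AEs will be collected from catheter placement through the end of study visit", and SAP 6.2 agrees: "all AE collection start from date/time of catheter placement". Protocol 8.2.1.1 uses the same anchor: a pre-existing condition becomes a treatment-emergent event only if it worsens during or after placement. Protocol 7.5.1.2 gives an earlier start: "AEs will be recorded from the time of signing the informed consent document".

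**Attribution.** Protocol 8.2.2.1 asks for relatedness to the drug and, separately, to the surgical and infusion procedure, and it distinguishes events before the start of infusion from later ones. Protocol 9.2.6 plans some summaries by relationship to infusion and catheter placement.

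**Surgery without drug.** Protocol 7.5.2.3 covers the case where every catheter is misplaced or unusable: "the procedure will be halted and no infusion" is given. It calls this unlikely.

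**Who is in the safety set.** Protocol 9.2.2.4 reads: "The Safety population will comprise all patients treated on study". Protocol 8.2 reads: "Each subject receiving MDNA55 via CED will be evaluable for safety". Protocol 9.2.2.1 assigns the drug-receiving ITT set to the primary efficacy analyses, "other purely survival-based endpoints and all safety analyses". SAP 5.1, whose heading merges ITT and Safety, takes subjects "who sign the ICF and who receive any amount of study drug". SAP 7.8 runs every safety analysis on the safety population.

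**The concern.** The intervention is a neurosurgical delivery procedure together with a drug. The plan recognises this by opening the event window at surgery and asking about procedural causation. Entry to the analysis set then depends on something that happens after surgery, namely whether infusion starts. A subject can therefore have a recorded, treatment-emergent, procedure-related event and still be counted in no safety table.

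Exclusion follows from the procedure failing, so it need not be unrelated to procedural harm. The secondary objective is safety following convection-enhanced delivery, and that delivery cannot be given without the surgery. A single-arm study also has no control group in which the gap would show.

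**Working it through.** The plan states no figure on this point, so there is none to reproduce. The check sets the rules side by side and then sizes the effect under stated assumptions.

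**Step 1: does the entry rule really require drug?** The word treated in Protocol 9.2.2.4 could be read to include surgery alone. Protocol 8.2, Protocol 9.2.2.1 and SAP 5.1 each tie the set to receipt of drug, which settles the reading.

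**Step 2: follow one subject through the plan.** Take a subject with catheters placed and infusion never started.

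| Rule | Result for this subject |
|---|---|
| Event window (Protocol Table 7 note o; SAP 6.2) | Open; events are recorded |
| Procedure attribution (Protocol 8.2.2.1) | Applies |
| Safety population (SAP 5.1) | Not a member |
| Safety summaries (SAP 7.8) | Not counted |
| Serious event reporting (Protocol 8.2.2.4) | Reported individually, whatever the relation to drug |
| Disposition (SAP 7.2) | Enrolled but not treated; no operated-but-not-infused category |
| Deviations (SAP 7.3) | Included if a deviation is recorded |

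SAP 7.2 dates enrolment from consent, so enrolled minus treated mixes subjects who never reached surgery with those who did. It also tabulates reasons for discontinuation for treated subjects only.

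**Step 3: direction.** Let N be the subjects operated on, m those not infused, x the infused subjects with a procedural event and k the non-infused subjects with one.

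- Rate in the safety set: x/(N − m)
- Rate among all operated: (x + k)/N

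The second exceeds the first only when k/m is greater than x/(N − m), that is, when the event rate is higher in non-infused than in infused subjects.

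**Step 4: size.** The documents give none of N, m, x or k. Assume first that N = 52, the planned enrolment in Protocol 4.1, all operated on.

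- m = 1, k = 1: the difference is (x + 1)/52 − x/51 = (51 − x)/2652. For x = 0, 2 and 5 this is 1.9, 1.8 and 1.7 points. With x = 2, the rates are 2/51 = 3.9% and 3/52 = 5.8%.
- m = 1, k = 0, x = 2: 2/51 = 3.9% against 2/52 = 3.8%. The safety-set rate is then slightly too high.
- m = 3, k = 3, x = 2: 2/49 = 4.1% against 5/52 = 9.6%.
- m = 3, k = 0, x = 2: 2/49 = 4.1% against 2/52 = 3.8%.

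With a smaller operated group of 47 (46 infused and one not) and x = 2, k = 1: 2/46 = 4.3% against 3/47 = 6.4%, again about 2 points.

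**The case against.** The other side has real points.

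- **The halting rule describes technical failure, not injury.** A reader might infer that a subject with a haemorrhage at placement is excluded because of that harm. It could happen, but Protocol 7.5.2.3 speaks of misplaced or non-functioning catheters, so this scenario is inference.
- **The affected group may be very small.** Drug and tracer are in the same infusate (Protocol 6.2), and convection is monitored after infusion begins (Protocol Table 6). A subject whose catheters prove not to convect at that stage has probably already received some drug and is in the set. The detailed workflow in Protocol Table 5 was not readable in the text used here, so the split cannot be settled.
- **A reader might take the gap between 52 enrolled and 46 evaluable as six failed placements.** Protocol 4.1 links that gap to evaluability for survival and not to surgery. Because enrolment is dated from consent, it may include subjects who never had an operation.
- **Nothing is concealed.** Events during placement go into the database (Protocol 7.5.2.2), serious ones are reported within 24 hours, and pre-infusion events in infused subjects are tabulated.
- **An exception may exist.** The SAP text used here passes from the opening of 7.8 to 7.8.2, so any rule in 7.8.1 could not be read. The general statement in 7.8 makes an exception unlikely but does not rule it out.

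These points limit the size and the certainty of direction. They do not remove the mismatch. Individual serious-event reports are not tabulation, and non-serious procedural events have no such route.

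**Conclusion.** The mismatch stands in both documents. Followed as written, the plan records procedural events in operated-but-not-infused subjects and leaves them out of the safety summaries, subject to the unread SAP 7.8.1.

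That procedural risk is understated is a plausible expectation, not an established fact. It requires a higher event rate among non-infused subjects, and if they have no events the reported rate is marginally too high. With one such subject who has an event, the shift is about 2 percentage points. More such subjects with events would shift it further, but the documents give no count and describe the situation as unlikely. The survival analysis and its sample size are unaffected. This is a small gap worth closing, because exclusion depends on the procedure failing.

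**What to change.** 1. Keep the drug-treated set for overall survival, drug-related events and the general safety tables. Replacing the whole safety population is unnecessary.
2. Add to SAP section 5 a procedural-safety set: all subjects in whom catheter placement was started, whether or not infusion followed.
3. Tabulate procedure-related events on that set. Limit the table to a defined peri-procedural period, or state the follow-up for each group. Protocol 4.4 directs follow-up of subjects who receive MDNA55 and Protocol 7.5.3 times visits from infusion, so non-infused subjects have no defined visit schedule.
4. Add an operated-but-not-infused line to the disposition table in SAP 7.2. If there are none, the line will show it.
5. Reconcile the start of event collection between Protocol 7.5.1.2 (consent) and Table 7 note o with SAP 6.2 (catheter placement).

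The cost is SAP wording before database lock, one extra denominator and one extra table. Events at placement are already captured. The drawback is unequal follow-up within the new set, which is why step 3 restricts the period or requires follow-up to be stated.

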7.5.2.4 End of CED Infusion (Day 1 - 2)

These procedures must be completed at the end of the CED infusion (see Section 6.3):

A standard 12 Lead ECG (triplicate assessment) will be performed immediately following

completion of the infusion (within 2 hours)

Version: v.6.1

MRI for final evaluation of drug distribution (with catheters maintained in place) will be performed within 4 hours (ideally within 2 hours) following completion of infusion

- o Removal of catheters and closure of incisions in accordance with institutional practice at bedside. NOTE: catheters are only removed after the end of infusion MRI is performed.
- Collection of blood samples for PK analysis as soon as possible but not more than 1 hour following infusion end time, approximately 3 hours following completion of infusion and then (after the ~3 hour sample collection) every 6 hours ± 2 hours until 24 hours or until subject is discharged from the hospital (whichever occurs first)
- Blood samples for hematology, serum chemistry, and coagulation (Section 7.2.1) shall be taken in parallel with either the PK blood collection that is performed within 1 hour following completion of infusion or the PK blood collection that is performed ~3 hours following completion of infusion.
- MRI performed within 18-30 hours after infusion end time to assess non-specific enhancement following the infusion
- Brief medical history and physical and neurological examinations including KPS, noting any changes since prior to study drug administration shall be performed when the subject is ambulatory prior to hospital discharge.
- Vital signs (pulse, respiratory rate, blood pressure and weight) taken when the subject is ambulatory prior to hospital discharge.
- Any AEs and new concomitant medications and/or changes to concomitant medications will be recorded throughout entire hospitalization period.

7.5.3 **Post-Treatment Follow-up Assessments**

Assessment of safety will be performed on Day 14 (± 3 days) after infusion. Both efficacy and safety assessments will be performed on Days 30 (± 3), 60 (± 7), 90 (± 7) and 120 (± 7) and every 8 weeks (± 7) thereafter until at least 360 days of active follow up have been completed after start of infusion. Unscheduled MRI exams may be required for confirmation of overall response status when preliminary CR or PR or PD by repeat assessment 4 weeks (or at appropriate interval for post bevacizumab (Avastin®) therapy) after it is observed (required if preliminary response or preliminary progression is observed at Day 120, 180, 240, 300 or 360). Subjects who undergo

Protocol # MDNA55-05 Version: v.6.1

post-treatment surgery to de-bulk the tumor, and if the tumor is shown to be largely necrotic with no viable tumor, will continue to be followed for tumor recurrence by MRI at the scheduled visits in order to establish PFS.

Subjects who complete the Day 360 assessment without disease progression or discontinue early without disease progression will continue to be followed for disease status until progression where possible. After progression (on study or during post-study follow-up), subjects will continue to be followed (by access of available medical records or via periodic telephone contact to the subject/caregiver), where possible, for survival, post-study treatment(s) for GB and imaging for GB until death (or termination of data collection by the Sponsor or withdrawal of consent by the subject).

7.5.3.1 14 Days (± 3 days) After Infusion

Subjects will return 14 (± 3) days after infusion.

Concomitant medications/therapies and AEs will be assessed by asking non-leading questions, and the following procedures will also be performed:

- Vital signs (pulse, respiratory rate, weight and blood pressure)
- Physical and neurological examinations including KPS
- Hematology, serum chemistry, and coagulation (Section 7.2.1)
- Collection of a blood sample for immunogenicity;
- Collection of a blood sample for PK

7.5.3.2 Follow up (for period of 12 months After Infusion)

Following completion of infusion, subjects will return on Days 30 (\pm 3), 60 (\pm 7), 90 (\pm 7) and 120 (\pm 7), and every 8 weeks (\pm 7) thereafter until Day 360 to undergo follow-up MRI. For sites that may use TRAMs, delayed contrast extravasation MRI can be performed on Days 30, 60, 90, 120 and 180 for calculation of TRAMs image map to be used for exploratory analyses of tissue response (calculation of TRAMs may be performed at the other follow up visits as or if requested by the Investigator).

At all of the above-named visits concomitant medications/therapies and AEs will be assessed by asking non-leading questions, and the following procedures will also be performed:

Physical and neurological examinations including KPS

- Vital signs (pulse, respiratory rate, weight and blood pressure)
- Hematology, serum chemistry, and coagulation (Section 7.2.1)
- Serum pregnancy test (female subjects; Day 30 and Day 180 visits only)
- Collection of blood samples for immunogenicity (Day 30, Day 120, Day 240 and Day 360 or early termination)

At any time-point during the follow-up period, should analyses on tumor tissue sample material occur at the discretion of the Investigator (e.g. biopsies to establish tissue response status), result should be recorded and material retained for biomarker analysis, where possible.

Other assessments will be performed at the Investigator's discretion and as necessary to follow up any AEs previously recorded.

The Day 360 visit will be equivalent to the early termination visit and will end the subject's safety reporting.

7.5.4 Early Termination Visit

Subjects who discontinue before the Day 360 visit will undergo all the procedures scheduled for the Day 360 visit if early termination is between follow-up visit time points. A new / repeat MRI will not be required if the last MRI performed was within 2 weeks prior to the early termination date, results from this prior MRI will be carried forward for the early termination assessment. When early termination is within 2 weeks following study follow up visit time point (i.e. Day 30, 60, 90, 120, 180 or 240) that visit will be considered the early termination time point and no additional assessments beyond the respective visit date assessments will be required. In the event that a subject is withdrawn from the study prior to the Day 360 visit, post-study follow-up should ensue (see Section 7.5.5 below).

7.5.5 Post-Study Follow-Up

Subjects who complete the Day 360 assessment without disease progression or discontinue early without disease progression will continue to be followed for disease status until progression where possible. After progression (on study or during post-study follow-up), subjects will continue to be followed (by access of available medical records or via periodic telephone contact to the subject/caregiver), where possible, for survival, post-study treatment(s) for GB and imaging for GB until death (or termination of data collection by the Sponsor or withdrawal of consent by the subject).

7.6 Usage of Concomitant Medications

All concurrent medical conditions and complications of the underlying malignancy will be treated at the discretion of the Investigator according to acceptable local standards of medical care. Subjects should receive analgesics, antiemetics, antibiotics, anti-pyretics, and blood products as necessary. Although warfarin-type anticoagulant therapies are permitted, careful monitoring of coagulation parameters is imperative to avoid complications of any possible drug interactions. All concomitant medications, including transfusions of blood products, will be recorded in the EDC system.

Guidelines for treating certain medical conditions are discussed below; however, institutional guidelines for the treatment of these conditions may also be used. The concomitant therapies that warrant special attention are discussed below.

